Unless otherwise stated, timings of efficacy endpoints will be relative to the date of randomization. Specifically, for all time-to event analyses (defined as [event date – randomization date] +1 where event occurs and as [appropriate censoring date based on analytic population – randomization date] +1 where event does not occur), the treatment groups will be analysed using a Cox proportional hazards model that includes treatment as an explanatory factor, region as stratification factors along with pre-specified baseline covariates: age, sex, ejection fraction, NYHA class, heart failure etiology (Ischemic vs. non-ischemic (unknown etiology considered as non-ischemic)), NT-proBNP, haemoglobin, ferritin, TSAT, eGFR and BMI, unless specified otherwise. If any of the pre-specified baseline covariates have >5 participants with missing data, they will not be used in the analyses to maintain the ITT population for the model. If the baseline covariate is missing data on ≤ 5 participants, we will impute the missing value with overall mode if categorical covariate and the overall mean if continuous variable. The Efron method will be used for handling ties. P-value and confidence intervals for the HR will be based on the Wald statistic. Any analyses using events that are confirmed by the CEC will use the CEC adjudicated responses and related dates. Analyses of Cardiovascular (CV) death, will include deaths with cause of death confirmed as unknown. In addition, the summary tables of these analyses will include the number of participants with event and the cumulative incidence (1 – the “survival” or event-free proportion) over time per treatment group presented annually through the last time point where 90% of the overall events have occurred. Cumulative incidence function and Kaplan-Meier estimates of participants with events will also be calculated and plotted through maximum follow up available in the study, with number of participants at risk indicated below the plot at specific times.

We will present empirical cumulative distribution function curves by treatment of change in 6MWT distance at 6 and 12 months.

For all the hierarchical composite endpoints, in addition to primary analytic method, we will present win-ratio along with its confidence interval.

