4.3 Right Censoring

In this study we expect missing outcome data to be infrequent and every effort will be made to collect all information regarding the primary outcomes prior to study termination, even in those who have discontinued the study treatment.

For all analyses covered by this SAP, the observation time for participants who have not had an event in the analysis of a specific outcome will be right censored at the date of last contact where any elements of the outcome could be assessed unless otherwise specified. Same algorithm will be followed for inclusion of events in the analyses.

Note that for the analysis of the components of the primary composite outcome, participant exposure will be censored at the date of the occurrence of the component outcome of interest.

Note that for outcomes not including CV death, all deaths are censoring events.

In safety time-to-event analyses in the Safety population, participants who have not had the event in question will be censored following same rules as detailed for the ITT population.

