5.7 Exploratory Analyses

The below endpoints will be explored to further help interpret the primary analyses. All analyses will be conducted in ITT population only.

- (1) Time to all cause death at one year defined as time from randomization to all cause death within 1 year (non-events censored at 1 year) will be compared using the Cox proportional hazards model.
- (2) Number of heart failure hospitalizations at one year will be analysed using negative binomial regression analysis.
- (3) Combination of all cause death and number of heart failure hospitalizations at one year will be analysed using the same method as used for the primary efficacy endpoint.
- (4) Mean change in the 6MWT distance from baseline to six months will be compared using linear regression adjusting for baseline value of 6MWT distance and region. To assess change from baseline, a baseline measurement and the 6-month measurement both are required
- (5) Time to all cause death through the duration of the study defined as time from randomization to all cause death (non-events censored at last known alive date) will be compared using the Cox proportional hazards model.

- (6) Combination of CV death and total number of heart failure hospitalizations through the duration of the study will be analysed using the same method as used for the primary efficacy endpoint.
- (7) Combination of CV death and total number of urgent heart failure visits through the duration of the study will be analysed using the same method as used for the primary efficacy endpoint.
- (8) Combination of investigator-reported events of cardiovascular death and number of heart failure hospitalizations at 1 year and change in 6-minute walk distance (6MWD) at 6 months using the same method as for the primary efficacy endpoint.
- (9) Time to first investigator-reported cardiovascular death or hospitalization for heart failure will be compared using the Cox proportional hazards model.
- (10) Days alive and out of hospital (any cause) at 1 year as reported by investigator will be summarized overall and by region. It will be compared using a modified Poisson approach.
- (11) Mean change in the 6MWT distance from baseline to 12 months will be compared using linear regression adjusting for baseline value of 6MWT distance and region in the subset of population with NYHA class of III/IV at baseline. To assess change from baseline, a baseline measurement and the 12-month measurement both are required

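### For outcomes with a competing death, the annual cumulative incidence in SAP v1.3 is 1 minus Kaplan-Meier with those deaths censored, so the tabulated absolute risks are somewhat too high

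*Combined protocol and SAP*

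**What the plan says.** All references are to SAP v1.3.

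- **Table (section 4.1).** The summary tables give "the number of participants with event and the cumulative incidence". The parenthesis that follows defines cumulative incidence as 1 minus the survival "or event-free proportion) over time per treatment group presented annually through the last time point where 90% of the overall events have occurred".
- **Plots (section 4.1, next sentence).** "Cumulative incidence function and Kaplan-Meier estimates of participants with events will also be calculated and plotted", through the maximum follow-up available. No estimator is named for the cumulative incidence function.
- **Deaths, outcomes without CV death (section 4.3).** "Note that for outcomes not including CV death, all deaths are censoring events". This covers hospitalization for MI, for stroke and for other CV events, and urgent heart failure visits (section 5.5, items 6-9). For non-CV death (item 5) it can only sensibly mean CV deaths.
- **Deaths, outcomes with CV death (section 4.3).** There is no specific sentence on non-CV death. The general rule applies: a participant without the event is "right censored at the date of last contact where any elements of the outcome could be assessed unless otherwise specified".
- **Undetermined deaths (section 4.1).** "Analyses of Cardiovascular (CV) death, will include deaths with cause of death confirmed as unknown".

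The SAP does not mention competing risks.

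**The concern.** A participant who dies of another cause can no longer be hospitalized for MI or die a CV death. Censoring such a death treats the participant as if the event could still occur later. One minus Kaplan-Meier then describes the risk that would apply if the competing deaths were removed, not the proportion who have the event. It is the larger of the two wherever competing deaths occur, and the gap widens with follow-up.

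The plan assumes 8% control-arm mortality in the first year, so the gap is not negligible for the outcomes that exclude death. Absolute risks by arm, and the risk differences taken from them, are what clinicians read from these tables.

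**Working it through.** **Inputs (SAP v1.3 section 1.4).** Top secondary control rate 0.0128 per month; hazard ratio 0.80, so 0.01024 per month on treatment; uniform accrual over 30 months; follow-up 12 to 42 months; loss 0.0021 per month; 3014 participants; one-year all-cause death 8% control and 6.8% treatment. Assumed, because the documents do not give them: the non-CV share of deaths (10-30%), the rates of the single non-fatal outcomes (1-10% per year), and constant hazards.

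**1. The plan's own figure.** Expected events per arm are n × λ/(λ+η) × [1 − (e^(−12(λ+η)) − e^(−42(λ+η)))/(30(λ+η))], with η = 0.0021. With 1500 per arm this gives 419.6 + 347.6 = 767. With 1507 per arm it gives 771, the stated number. The inputs are therefore read as the plan meant them.

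**2. The two estimates.** The death hazard is −ln(0.92)/12 = 0.00695 per month (control) and −ln(0.932)/12 = 0.00587 (treatment). For event hazard h and competing hazard c:
- tabulated value: 1 − e^(−ht)
- actual cumulative incidence: h/(h+c) × [1 − e^(−(h+c)t)]

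**3. Non-fatal outcomes, all deaths competing (c = 0.00695).** Each cell gives 1 minus Kaplan-Meier, then actual incidence, in %.

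| Month | 1%/year | 5%/year | 10%/year | Relative excess |
|---|---|---|---|---|
| 12 | 1.00, 0.95 | 4.88, 4.68 | 9.52, 9.14 | 4.2% |
| 24 | 1.98, 1.82 | 9.52, 8.78 | 18.13, 16.74 | 8.3-8.5% |
| 36 | 2.96, 2.62 | 13.93, 12.36 | 25.92, 23.07 | 12.3-13.0% |

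**4. Top secondary, control arm.** Here c is 10-30% of 0.00695. For example, at 24 months with 20%, c = 0.00139 and 0.0128/0.01419 × (1 − e^(−0.3406)) = 26.04%, against 26.45% by 1 minus Kaplan-Meier.

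| Month | 1 − KM | Actual (10% to 30% non-CV) | Excess, points | Risk difference between arms: 1 − KM, actual |
|---|---|---|---|---|
| 12 | 14.24% | 14.18-14.07% | 0.06-0.17 | 2.68, 2.66-2.62 |
| 24 | 26.45% | 26.24-25.83% | 0.21-0.62 | 4.66, 4.60-4.48 |
| 36 | 36.92% | 36.50-35.67% | 0.42-1.25 | 6.09, 5.97-5.74 |

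**5. Other outcomes.** For non-CV death, with CV death competing, the relative excess is 2.9-3.8% at 12 months and 8.9-11.6% at 36 months over the same 10-30% range. For all-cause death nothing competes, so c = 0 and the two formulas are identical.

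**6. Where the annual table stops.** It runs to the last time point at which 90% of events have occurred. Under the planned accrual, the share of participants whose scheduled follow-up reaches month u is 1 up to 12 and (42 − u)/30 after that. Integrating λe^(−(λ+η)u) times this share, over both arms, puts about 84% of top secondary events by month 24, 90% by month 27.6 and 98% by month 36. For the rarer outcomes, with death competing, the 90% point is at months 27-28. On the natural reading the last annual row is therefore month 24.

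**The case against.** The strongest reply is that section 4.1 already provides both estimates. A reader might infer that table and figure are bound to disagree. The documents do not support that: the same sentence plots Kaplan-Meier estimates, which the table would match. A mismatch with the plotted cumulative incidence function arises only if that function is a competing-risks estimate. SAP v1.0 section 4.1 listed only a cumulative incidence function and v1.3 added Kaplan-Meier beside it, which suggests two estimators, but the text does not say so. If the function is simply 1 minus survival, there is no mismatch, and no competing-risks estimate is planned either.

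Three further points stand:

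- The largest excesses probably never reach the annual table, given the 90% cut-off. The 36-month figures apply mainly to curves drawn as 1 minus Kaplan-Meier, or to longer follow-up than planned (section 1.4 sets no required maximum).
- For the top secondary outcome, the only time-to-event outcome with allocated alpha, the excess is small. Counting undetermined deaths as CV reduces it further. Censoring of non-CV deaths there is inferred from the general rule, not stated.
- The output is descriptive. The most affected outcomes are described as supportive in section 5.5, and the tables also give the number of participants with events.

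None of this removes the bias in the figure that section 4.1 labels cumulative incidence. The label and formula are explicit, and for outcomes excluding CV death so is the censoring.

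**Conclusion.** The point holds as a minor one. Following sections 4.1 and 4.3 as written gives absolute risks that are too high for every outcome with a competing death. In the rows the annual table is likely to contain, the relative excess is about 4% at 12 months and 8% at 24 months for MI, stroke, other CV hospitalization and urgent heart failure visits. For the top secondary outcome it is about 0.06-0.17 points at 12 months and 0.2-0.6 at 24 months. These sizes rest on constant hazards, the plan's 8% annual mortality, assumed event rates of 1-10% per year and an assumed 10-30% non-CV share of deaths.

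Two broader readings should be resisted. Not every time-to-event outcome is affected: the all-cause death analyses in section 5.7, such as "time from randomization to all cause death (non-events censored at last known alive date"), have no competing death. Nor is the treatment comparison in doubt: the Cox hazard ratios, p-values, alpha, sample size and the 771-event target are unchanged.

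**What to change.** In section 4.1, define the tabulated and plotted cumulative incidence as the Aalen-Johansen estimate and name the competing event for each type of outcome:

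- non-CV death, for outcomes that include CV death;
- all death, for outcomes that exclude death;
- CV death, for the non-CV death outcome.

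Use the same estimate in tables and plots. Kaplan-Meier curves may stay as a labelled supplement. In section 4.3, state the handling of non-CV death explicitly for outcomes that include CV death, and say that the censoring there applies to the Cox models.

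The cost is a few lines of SAP text and a programming option. No new data are needed, and the only downside is slightly lower stated absolute risks.

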Initial treatment will occur on Day 0 (date of randomization) and Day 7. On Day 0 and Day 7, Group A (FCM) will receive a 750 mg undiluted blinded dose of IV FCM at the rate of approximately 100 mg (2 mL)/minute; Group B (placebo) will receive a blinded placebo (15 cc of normal saline) IV push at 2 mL/minute. Participants in Group A with body weight <50 kg (110 pounds) will have individual FCM doses adjusted to 15 mg/kg, not to exceed an individual dose of 750 mg, or a cumulative dose of 1500 mg per treatment cycle.

All participants will be dosed every 6 months for the duration of the trial. Participants randomized to the FCM arm will be dosed as indicated based on hemoglobin (Hgb) levels (i.e. Hgb <13.5 g/dl [females] or <15.0 g/dl [males])) and iron studies (i.e. serum ferritin <100 ng/mL or 100 to 300 ng/mL with TSAT <20%). Participants not meeting post- randomization lab criteria for blood counts and iron studies and all participants randomized to the placebo arm will be administered IV placebo at each visit.

Unblinded site personnel, responsible for preparation and administration of the FCM or Placebo, will ensure that the participant and all blinded site staff are not able to observe the preparation or administration of study treatment.

**Patient
Assessments**

Efficacy and Safety Follow-up: All participants will be followed from the time of randomization until completion of the trial. The last participant randomized will be followed for 12 months. After treatment on Day 0 and Day 7, participants will be evaluated at 3 month intervals (in person or via telephone), with additional dosing administered every 6 months as applicable (see Section 3.1). Hematology, ferritin, and transferrin saturation (TSAT) laboratory assessments will be performed in all participants, with appropriate safety evaluations, to determine if additional treatment will occur at 6 month intervals. At the conclusion of the study all participants will be assessed for the occurrence of any potential endpoint or serious adverse events. Attempts to determine Vital Status, including endpoint ascertainment, for participants who are lost to follow-up or withdrawn will be made via a search of available public records, and other appropriate investigative techniques, including the potential use of third party vendors as described in the informed consent form and in accordance with applicable regulatory requirements.

**Primary
Endpoint:**

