4.4 Withdrawal from Study

Any participant who wishes to withdraw from the study may do so at any time without the need to justify their decision. The investigator may withdraw a participant from active study treatment at any time if it is felt to be in the best interest of the participant

At time of withdrawal from the study, procedures for the Termination visit must be immediately performed regardless of whether the participant has completed study drug treatment. Information collected previously as part of the study will be retained unless the patient specifically withdraws consent, in writing. The participant should be contacted at the end of the study to assess for the occurrence of any potential endpoint events. Additionally, if the participant cannot be contacted, attempts to determine the Vital Status will be performed via a search of available public records, third party vendor search, medical record review, additional contacts provided by the patient, and other appropriate investigative techniques as described in the informed consent form and in accordance with applicable regulatory requirements.

In event of site closure, participants may be asked to agree to follow up at another research site, if available, or for follow up by a patient follow-up group.

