8.9 Handling of Missing Data

Every effort will be made to limit the number of missing data points. The trial will be conducted in jurisdiction which will allow ascertainment of vital status even in individuals who discontinue the study. Participants who discontinue taking study drug should be encouraged to continue participation in the trial so that endpoint data can be collected.

Furthermore, consent will be obtained to examine hospital records where feasible. Partnership with transportation companies will be fostered to decrease the burden of travel to clinic visit and increase the likelihood of the final study visit taking place.

The prospective plan for the handling of missing data is as follows:

The primary analysis will rely on a multiple imputation model, with Markov chain Monte Carlo algorithm based on the totality of observed data. One exception to this rule will be individuals unable to perform the 6MWT test at 6 months will have their value imputed as the worst observed change in 6MWT.

Two supporting analyses will be undertaken. The first one will use multiple imputation for clinical outcomes, but will impute the worst observed change in 6MWT to all individuals who do not have this measurement, regardless of the reason.

The second series of analyses will perform tipping point assessments to determine the sensitivity of the observed result to the missing data. Given the multi-dimensional nature of outcomes, tipping point analyses will be performed separately for each outcome: mortality, hospitalization for heart failure and 6MWT.

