The timing of safety data will be relative to the study drug start date. Specifically, any time to safety event durations will be defined as [event date – study drug start date] +1 where event occurs and as [appropriate censoring date based on analytic population – study drug start date] +1 where event does not occur).

Baseline is defined as response/value collected closest to randomization and on or prior to study drug start. If both date and time are available we will use the value prior to the first study drug start date time. However, if only dates are available, we will use the values on or prior to first study drug start date as the baseline. Any measures (for example central labs) without a value in this window will have a missing baseline value.

End of study date for the participant will be driven off of the date of their final study disposition. Date of last contact for the participant will be driven off of their last visit

performed, these dates can be different from the date last known alive collected on end of study form for withdrawn consent participants.

The median and total person-years of follow-up for the whole study will also be reported.

All analyses included in this SAP will be performed using SAS v9.4 or higher. They will be based on Clinical Data Interchange Standards Consortium (CDISC) standard data (Analysis Data Model (ADaM) and/or Study Data Tabulation Model (SDTM)). The summaries will be presented as either tables or, where appropriate, as figures. International Council for Harmonisation (ICH) required listings will also be produced.

- “n” will be displayed as a whole number
- The Mean, SD, Median, Q1, and Q3 will be displayed with 1 more decimal place than the source data precision.
- The Min and Max will be displayed with the same number of decimal places as the source data. Any other presentation of raw data will be also be displayed with the same decimal places as the source data.
- All tests and confidence intervals are 2-sided unless specified otherwise.
- All p-values will be displayed with three decimal places.
- All by visit summaries and analyses will use scheduled/nominal.

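### SAP v1.3 is inconsistent on whether a death known to have occurred after the last visit counts: dated deaths could be excluded while undated ones are included

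*Combined protocol and SAP*

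**What the plan says.** **Protocol v3 looks for these deaths.** The synopsis (Patient Assessments) states: "Attempts to determine Vital Status, including endpoint ascertainment, for participants who are lost to follow-up or withdrawn" will be made. Section 4.4 adds that if a withdrawn participant cannot be reached, "attempts to determine the Vital Status will be performed via a search of available public records", vendors and medical records. Section 4.6 continues the effort for lost participants until the trial ends. Section 8.9 relies on jurisdictions that permit "ascertainment of vital status even in individuals who discontinue the study".

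**SAP v1.3 sections 4.1 and 4.3 set a contact-based cut-off.** Section 4.1: "Date of last contact for the participant will be driven off of their last visit" performed. It then notes that "these dates can be different from the date last known alive collected on end of study form for withdrawn consent participants". Section 4.3 applies to every analysis in the SAP. The observation time of a participant without an event "will be right censored at the date of last contact where any elements of the outcome could be assessed unless otherwise specified". The next sentence reads: "Same algorithm will be followed for inclusion of events in the analyses".

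**SAP v1.3 sections 4.4.1 and 5.7 point the other way.** Under 4.4.1 a completely undated death is assigned to the day after last contact, and the date rules of that section apply to deaths in the primary analysis. Partly dated composite events may not be imputed beyond the last-known-alive date on the end-of-study form. In 5.7(5), all-cause death over the study has "non-events censored at last known alive date".

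**The concern.** Take a participant whose last visit is Day 90, who then withdraws, and whose confirmed death on Day 230 is found by the records search. Under 4.1 and 4.3 as worded, that death comes after last contact and is not included. Death is the first tier of the primary endpoint, so the participant moves from the worst tier to the survivors. With no heart failure hospitalization, the participant outranks every hospitalized survivor and every death, whatever walk distance is assigned.

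Nothing else in SAP v1.3 catches this. The multiple imputation in 4.4.1 covers only the 6-month walk distance, not clinical outcomes. The tipping-point analysis of the primary in 5.3.1.8 also covers only the walk test, although Protocol 8.9 calls for separate tipping-point analyses of mortality, hospitalization and walk test.

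At stake are the correct ranking of deaths the trial has gone to some trouble to find, agreement between the primary-tier deaths and the all-cause mortality table, and protection against bias if withdrawal, or mortality after it, differs between arms.

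**Working it through.** **1. The rules side by side (SAP v1.3)**

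| Situation | Section | What follows |
|---|---|---|
| Dated death after last visit, literal reading | 4.1 with 4.3 | Outside the window; ranked alive |
| Undated death | 4.4.1 | Dated one day past last contact and used in the primary |
| Partly dated composite event | 4.4.1 | Imputed date limited by last known alive, not by last visit |
| All-cause death, whole study | 5.7(5) | Non-events censored at last known alive |
| Tier 1 of the primary | 5.1 | Confirmed death at one year; no visit cut-off stated |

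Rows 1 and 2 conflict: a death with no date would count just past the cut-off, while a death with a known date past the same cut-off would not.

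**2. Inputs for the size of the problem.** SAP 1.4 gives 1507 per arm, 2.5% annual loss (0.0021 per month), and 12-month mortality of 8% (control) and 6.8% (treatment). The documents give no mortality after leaving, so a multiplier *k* on the trial hazard is assumed.

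Check of the plan's loss rate: −ln(1 − 0.025)/12 = 0.00211 per month, which agrees with 0.0021.

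Expected 12-month deaths: 1507 × 0.08 + 1507 × 0.068 = 120.6 + 102.5 = 223.

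**3. Deaths after leaving, within 12 months.** With η = −ln(0.975) = 0.0253 per year, and λ = −ln(0.92) = 0.0834 (control) or −ln(0.932) = 0.0704 (treatment), the expected number per arm is

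1507 × ∫₀¹ η e^(−(η+λ)s) [1 − e^(−kλ(1−s))] ds.

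For *k* = 1 this can be done by hand:
- Control: 1507 × (0.02399 − 0.975-complement term 0.025 × 0.92 = 0.02300) = 1507 × 0.00099 = 1.49.
- Treatment: 1507 × (0.02414 − 0.025 × 0.932 = 0.02330) = 1507 × 0.00084 = 1.27.
- Total: 2.76.

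The first term in each bracket is the probability of leaving alive within the year; over both arms it gives about 73 participants.

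| *k* (assumed) | Deaths after leaving, 12 months | Share of 223 |
|---|---|---|
| 1 | 2.8 | 1.2% |
| 2 | 5.4 | 2.4% |
| 3 | 7.9 | 3.5% |
| 5 | 12.5 | 5.6% |

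These are upper bounds, since they suppose the search finds and dates every such death.

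**4. Effect on the primary test.** The three-tier ranking was simulated at the planning rates (1000 trials per setting, Wilcoxon-Mann-Whitney, two-sided 0.0099), counting and then excluding these deaths.

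| *k* | Mean Z, counted / excluded | Power, counted / excluded |
|---|---|---|
| 1 | 5.11 / 5.11 | 99.4% / 99.4% |
| 3 | 5.12 / 5.13 | 99.5% / 99.6% |
| 5 | 5.15 / 5.15 | 99.8% / 99.8% |

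Only the differences are informative. These runs omit the plan's 15% missing walk tests and apply the same *k* and loss rate in both arms. The plan's stated 90% power was not reproduced: with 15% missing walk tests set to worst, a separate run gave 95.3%. The correlations between components are not in the documents.

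**The case against.** A reader might infer that the SAP will drop these deaths and rank the participants as survivors. The documents do not support that as a stated rule, for four reasons:

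- **The strict reading defeats itself.** No visit follows a death, so a last-visit cut-off on events would remove nearly all of the 223 expected deaths and empty tier 1. That cannot be intended.
- **The wording of 4.3 is qualified.** It censors those without an event, at the last contact where any element could be assessed, unless otherwise specified. A records search that establishes vital status can be read as assessing an element.
- **Other sections lean towards counting.** Section 4.1 uses the adjudicated date where an event occurs and a censoring date only where it does not. Section 5.1 has no visit limit. The treatment of undated deaths in 4.4.1 makes sense only if deaths after last contact count.
- **Last known alive is not confined to 5.7(5).** It also limits imputed dates in 4.4.1 and 4.4.2.

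All of this stands, and so does the objection that the expected numerical effect is small. Nothing in the documents shows that withdrawal will differ by arm.

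It does not remove the inconsistency. Section 4.3 covers all analyses and extends the cut-off to event inclusion in so many words, and no sentence expressly keeps a dated death found after the last visit. If the rule cannot be applied as written, the programmer must improvise. For a death during active follow-up the choice is obvious; for one found after withdrawal it is not.

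**Conclusion.** The concern holds as an internal inconsistency. Sections 4.1 and 4.3, followed as worded, exclude a dated death after the last visit; 4.4.1 and 5.7(5) imply that deaths after last contact count. Such deaths could therefore be excluded from the primary and from the CV-death analyses while undated ones are included. That they would be excluded is not established.

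The size is about 3 deaths in 12 months if mortality after leaving equals the trial rate, and 5 to 8 at an assumed two to three times that rate: about 1% to 3.5% of the expected 223. Power for the primary test does not materially change when loss and post-loss mortality multipliers are equal in the two arms; unequal withdrawal was not simulated and could introduce bias. It is worth correcting because it touches the top tier of the primary endpoint, no planned analysis of the primary would expose it, and the correction is cheap.

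**What to change.** Amend SAP 4.3, before unblinding, to state that:

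1. Every CEC-confirmed death dated within the analysis horizon (12 months for tier 1 of the primary, study end for time-to-death analyses) counts by its own date, whatever its source and whether or not it follows the last visit.
2. In time-to-death analyses, participants not known to have died are censored at the last-known-alive date. This must accompany item 1; otherwise deaths found by the search enter without the matching time at risk of those found alive.
3. The contact-based rule remains for heart failure hospitalizations.
4. The rule for CV death in the top secondary composite is named explicitly. The choice is not automatic there, because hospitalizations are not observed after last contact even when vital status is.

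Then align 4.1, 4.4.1 and 5.7 with this text.

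The cost is a few sentences, and the last-known-alive date is already collected on the end-of-study form. The drawback is a few more deaths of undetermined cause, which the existing rules count as cardiovascular.
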